1. OBJECTIVES

1.1 Study Design

The purpose of this study is to evaluate the feasibility, safety, and toxicity of an adenoviral mediated GMCSF vaccination strategy in stage IV colorectal cancer patients. The Phase I trial employing adenoviral mediated gene transfer in patients with metastatic melanoma demonstrated that a simplified method of vaccine production was feasible, safe and immunogenic. We now propose a Phase I study utilizing the same constructs and vaccine strategy aimed at treating patients who have undergone hepatic resection for their colorectal cancer metastases. Only patients with resectable liver metastases are eligible to participate since the resected liver metastasis will be used to construct the vaccine.

Subjects may be enrolled if they will be undergoing a hepatic resection for colorectal metastases at the MGH. We will analyze both toxicity and immunity in this patient cohort. If this trial reveals significant biologic activity without substantive toxicity, then these results would provide a foundation for undertaking a subsequent Phase III study testing the therapeutic efficacy of vaccination in the adjuvant setting.

Further, we will evaluate the biologic activity of this vaccination scheme in stage IV colorectal cancer patients with resected hepatic metastases. Blood, skin punch biopsies and tumor samples obtained during the course of immunization will function as critical reagents for detailed analysis of the vaccine-induced immune responses.

1.2 Primary Objectives

- 1.2.1 To determine the safety of 6 vaccinations with lethally irradiated, autologous colorectal cancer cells engineered by adenoviral mediated gene transfer to secrete GM-CSF in stage IV colorectal cancer patients who are completely resected.

1.3 Secondary Objectives

- 1.3.1 To determine the progression free survival and two-year survival of stage IV colorectal cancer patients vaccinated with lethally irradiated, autologous colorectal cancer cells engineered by adenoviral mediated gene transfer to secrete GM-CSF.
- 1.3.2 To evaluate the immune response elicited by the vaccine.

2. BACKGROUND

2.1 Study Agent(s)

A vaccine composed of cells from lethally irradiated, autologous colorectal cancer hepatic metastasis engineered by adenoviral mediated gene transfer to secrete GM-CSF (GVAX).

CONFIDENTIAL

This document is confidential. Do not disclose or use except as authorized.

2.2 Study Disease

2.2.1 Background of Chemotherapy for Colorectal Cancer

In the United States, colorectal cancer is the fourth most common malignancy and the second most frequent cause of cancer-related death.¹ In 2011, an estimated 141,210 cases of colorectal cancer will be diagnosed and 49,380 people will die from this disease. Metastases to the liver are identified in up to 25% of patients at the time of diagnosis¹. For the remaining patients anywhere from 50-70% of patients will develop hepatic metastases during follow-up¹. Surgical resection continues to be the only modality which can provide patients with a long term cure. Multi drug chemotherapy and targeted therapies have improved patients' survival and have converted patients from unresectable to resectable, but usually cannot offer a cure. Additionally, chemotherapy often causes steatosis and steatohepatitis which increases the morbidity and mortality of hepatic resections. In addition to the hepatic damage caused by chemotherapy, different agents result in a multitude of side effects which can limit their utility.

Adjuvant therapy has evolved in the past two decades for stage IV colon cancer from just 5-FU to the addition of Oxaliplatin, Irinotecan and numerous targeted agents. Current multi-drug regimens for metastatic colorectal cancer have improved the overall survival (OS) from 6 to 20 months or more³. One of the first positive phase III multi drug regimens added Irinotecan to 5FU (IFL), resulting in an improved overall survival from 14mo to 17mo⁴. Oxaliplatin was added to 5FU (FOLFOX) resulting in an improved progression free survival of nearly 3mo⁵. FOLFOX was found to be superior to IFL with an OS of 19.5months vs. 15months in the N9741 trial⁶. Subsequently FOLFOX and FOLFIRI were compared which demonstrated similar times to progression and overall survivals⁷.

In the randomized trial by Nordlinger et al perioperative chemotherapy surrounding hepatic resection did offer a 9.2% longer progression free survival than an operation alone². This data along with the now known hepatic toxicity of Oxaliplatin and Irinotecan, has prompted most clinicians to offer 6 cycles of chemotherapy followed by hepatic resection and an additional 6 cycles of chemotherapy post operatively. The majority of patients receive 5-FU with either Oxaliplatin and/or Irinotecan (FOLFOX, FOLFIRI, or FOLFOXIRI). Immunotherapy utilizing autologous hepatic colorectal cancer metastases has not been extensively explored. This clinical trial offers a novel immunotherapeutic strategy as an adjunct to conventional chemotherapy.

2.2.2 Anti-Colorectal Cancer Immune Responses

The role of immune cells in human neoplasia is unclear⁸. Tumor infiltrating lymphocytes in melanoma⁹, colorectal cancers¹⁰⁻¹² and ovarian cancer¹³ have been shown to inhibit tumor growth and are associated with improved prognoses. Recent data from Pages et al^{14,15} demonstrated a significant difference in DFS and OS between patients who had primary tumors with vascular emboli, lymphatic invasion and perineural invasion (VELIPI) after adjustment for TNM and Duke's stage (VELIPI + and -: DFS3.3 mo vs. 26.9mo and 5yr OS 12% vs. 32.4%, p<0.001). Interestingly, VELIPI- tumors were associated with a strong immune infiltrate. Specifically, VELIPI- tumors had increased T cell differentiation (CD45R0, CD45RA, CD27, CD28, CCR7, and CD127), increased evidence of T cell migration (CD62L-, CCR7, CD103, CD49d, CXCR3), increased evidence of T cell activation (HLA-DR, CD98, CD80, CD86, CD134), and increased effector memory T cells (CD45RO+CCR7-CD28-CD27-) (p<0.05). Additionally, a high density of memory T cells (CD45RO+) was associated with tumors without lymph node involvement and metastases (p<0.001). Lymphocytic and memory T cell infiltrates are prognostic biomarkers associated with longer survival of patients independent of other clinicopathologic factors such as MSI status, Kras, BRAF, PIK3CA mutations, etc^{16,17}.

2.3 Rationale

This recent data supports the idea that after antigen stimulation a small population of antigen-specific memory T cells remains in the tissue and may “control” the primary cancer from recurring. Notwithstanding these provocative data, most patients fail to develop anti-colorectal cancer responses that are sufficiently potent to prevent lethal tumor progression. The understanding that tumor cells generally stimulate poor antigen presentation has motivated the design of several new strategies to increase anti-tumor immunity^{18 19}. Among the approaches using gene transfer, [name] group at DFCI has demonstrated that vaccination with irradiated tumor cells engineered to secrete granulocyte-macrophage colony stimulating factor (GM-CSF) generates potent, specific, and long-lasting anti-tumor immunity in multiple murine models, including the B16 melanoma²⁰. Vaccination involves enhanced tumor antigen presentation by recruited dendritic cells and macrophages; the coordinated functions of CD4⁺ and CD8⁺ T cells, CD1d-restricted NKT cells, and antibodies mediate protective immunity^{20 21 18 22}.

Further, Phase I trials conducted by Drs. [name] and [name] at DFCI employing adenoviral mediated gene transfer in patients with metastatic melanoma demonstrated that a simplified method of vaccine production was feasible, safe and immunogenic. We now propose a Phase I study utilizing the same constructs and vaccine strategy aimed at treating patients who have undergone hepatic resection for their colorectal metastases.

First, we will evaluate the feasibility, safety, and toxicity of this vaccination strategy in stage IV colorectal cancer patients. Subjects may be enrolled if they will be undergoing a hepatic resection for colorectal metastases at MGH. We will analyze both toxicity and immunity in this patient cohort. If this trial reveals significant biologic activity without substantive toxicity, then these results would provide a foundation for undertaking a subsequent Phase III study testing the therapeutic efficacy of vaccination in the adjuvant setting.

2.4 Correlative Studies Background

We will evaluate the biologic activity of this vaccination scheme in stage IV colorectal cancer patients with resected hepatic metastases. Prior to liver resection, blood samples will be collected and fresh frozen tissue from the hepatic metastases will be stored. Blood and skin punch biopsies obtained during the course of immunization, and pre-immunization tumor samples will function as critical reagents for detailed analysis of the vaccine-induced immune responses. Biopsies will be obtained two days after the first and fifth vaccinations. Specifically, we will evaluate the immune cell composition (CD4+ and CD8+ T cells, T regulatory cells, macrophage, etc) in the resected specimens and in the circulating blood. ELISPOTs will be performed to evaluate the specificity of the CD8+ T cell response to known colorectal cancer antigens. In patients with recurrent disease, biopsy of recurrence may also be evaluated when clinically appropriate.

3. PARTICIPANT SELECTION

3.1 Eligibility Criteria

Participants must meet the following criteria on screening examination prior to their planned liver resection to be eligible to participate in the study:

3.1.1 Stage IV patients must have:

- A) Histologically documented hepatic colorectal cancer metastasis
- B) Resectable hepatic lesion(s) as judged by PI or surgeon with the intent of an R0 resection.
- C) Primary tumor previously resected or planned resection at time of hepatic surgery

3.1.2 ECOG Performance Status 0 or 1

3.1.3 Age \geq 18 years

3.1.4 Patients may receive chemotherapy (FOLFOX, FOLFIRI, FOLFOXIRI) after their hepatic resection, but must be \geq 4 weeks from the last dose of chemotherapy in order to be eligible to receive vaccine.

- 3.1.5 Patients must be fully recovered from their hepatic resection per their surgeon or the study PI.
- 3.1.6 Participants must be \geq 4 weeks from chemotherapy, radiotherapy, immunotherapy, systemic glucocorticoid therapy or the operation to receive the first vaccine dose.
- 3.1.7 Must be able to understand and willing to sign a written informed consent document.
- 3.1.8 The primary colorectal cancer must be resected before hepatic resection or at the time of hepatic resection.
- 3.1.9 Laboratory values must demonstrate:
 - A. Total bilirubin \leq 2.0mg/dl
 - B. AST (SGOT) \leq 9 x ULN
 - C. ALT (SGPT) \leq 9 x ULN
 - D. Alkaline Phosphatase \leq 3 x ULN
 - E. Creatinine \leq 2.0 mg/dl

- 3.1.10 Negative Serum pregnancy test in women of childbearing potential.

3.2 Exclusion Criteria

Participants who exhibit any of the following conditions at screening will not be eligible for admission into the study.

- 3.2.1 Uncontrolled active infection
- 3.2.2 Infection with HIV, Hepatitis B or C
- 3.2.3 Other current malignancies except any *in situ* cancer or basal or squamous cell carcinoma
- 3.2.4 Active autoimmune disease including but not limited to: ALS, MS, SLE
- 3.2.5 Active corticosteroid therapy
- 3.2.6 Hepatic metastases involving both branches of the portal vein (right and left) or all three hepatic veins (left, middle and right)

- 3.2.7 Peritoneal metastases identified at the time of attempted resection
- 3.2.8 Residual/recurrent disease
- 3.2.9 Pregnant and or nursing women are excluded from this study because GM-CSF based vaccines have not been performed in animal or human reproduction studies. It may have potential for teratogenic or abortifacient effects. Because there is an unknown but potential risk of adverse events in nursing infants secondary to treatment of the mother with GM-CSF, breastfeeding should be discontinued if the mother is treated with GM-CSF. These potential risks may also apply to other agents used in this study.
- 3.2.10 Greater than 1 month since resection of liver metastasis for vaccine production.

4. REGISTRATION PROCEDURES

4.1 General Guidelines for DF/HCC and DF/PCC Institutions

Institutions will register eligible participants with the DF/HCC Quality Assurance Office for Clinical Trials (QACT) central registration system. Registration must occur prior to the initiation of therapy. Any participant not registered to the protocol before treatment begins will be considered ineligible and registration will be denied.

A member of the study team will confirm eligibility criteria and complete the protocol-specific eligibility checklist.

Following registration, participants may begin protocol treatment. Issues that would cause treatment delays should be discussed with the Principal Investigator. If a participant does not receive protocol therapy following registration, the participant's protocol status must be changed. Notify the QACT Registrar of participant status changes as soon as possible.

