4.2 Registration Process for DF/HCC and DF/PCC Institutions

The QACT registration staff is accessible on Monday through Friday, from 8:00 AM to 5:00 PM Eastern Standard Time. In emergency situations when a participant must begin treatment during off-hours or holidays, call the QACT registration line at [contact] and follow the instructions for registering participants after hours.

The registration procedures are as follows:

1. Obtain written informed consent from the participant prior to the performance of any study related procedures or assessments.
2. Complete the protocol-specific eligibility checklist using the eligibility assessment documented in the participant's medical/research record. **To be**

eligible for registration to the study, the participant must meet each inclusion and exclusion criteria listed on the eligibility checklist.

Reminder: Confirm eligibility for ancillary studies at the same time as eligibility for the treatment study. Registration to both treatment and ancillary studies will not be completed if eligibility requirements are not met for all studies.

3. Fax the eligibility checklist(s) and all pages of the consent form(s) to the QACT at [contact].
4. The QACT Registrar will (a) validate eligibility, (b) register the participant on the study, and (c) randomize the participant when applicable.
5. The QACT Registrar will send an email confirmation of the registration and/or randomization to the person initiating the registration immediately following the registration and/or randomization.

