14.3 Reporting and Exclusions

- 14.3.1 **Feasibility**- Feasibility will be defined by the capacity for patients in this specific population to initiate the vaccination process, i.e., to receive at least one vaccination. This will be governed by the ability to successfully harvest a minimum number of viable tumor cells at the time of surgery.

At the treating physician's discretion, patients with progressive disease or treatment-related complications between surgery and initiation of vaccination who are deemed incapable of or inappropriate for treatment will not initiate vaccination and will be included in the feasibility analysis.

We will consider this treatment plan feasible in this patient population if at

least 60% of initially enrolled patients go on to begin vaccination.

If an enrolled patient withdraws from the study for a reason that is not associated with surgical morbidity or disease progression, that patient will not be counted in the feasibility analysis.

14.3.2 **Safety and Biologic Activity:** All participants who receive at least one vaccine will be considered evaluable for toxicity. All participants who receive all 6 vaccines will be evaluable for biologic response.

14.3.3 **Evaluation of response.** All participants included in the study must be assessed for response to treatment, even if there are major protocol treatment deviations or if they are ineligible. Each participant should be assigned one of the following categories: 1) complete response, 2) partial response, 3) stable disease, 4) progressive disease, 5) early death from malignant disease, 6) early death from toxicity, 7) early death because of other cause, or 9) unknown (not assessable, insufficient data). By arbitrary convention, category 9 usually designates the "unknown" status of any type of data in a clinical database.

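### The plan conflicts on whether registration comes before or after the hepatic resection, so early post-operative failures could be left out of the feasibility denominator.

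*Combined protocol and SAP*

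**What the plan says.** **Registration.** Section 4.1: "Registration must occur prior to the initiation of therapy". Section 4.2 adds that, to be registered, "the participant must meet each inclusion and exclusion criteria listed on the eligibility checklist". Neither section mentions the resection. The treatment described in 5.1.2 is the vaccine, and 5.2 places the resection under pre-treatment criteria, so the start of therapy is most naturally the first vaccine.

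**Timing of eligibility.** Section 3.1 opens: "Participants must meet the following criteria on screening examination prior to their planned liver resection". Section 1.1 likewise describes enrolment of people whose resection is still to come.

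**Criteria that look past the operation.** The inclusion list under that heading contains 3.1.5: "Patients must be fully recovered from their hepatic resection per their surgeon or the study PI". The exclusions contain 3.2.7, "Peritoneal metastases identified at the time of attempted resection", then residual or recurrent disease (3.2.8), and more than one month having passed since the resection (3.2.10).

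**Denominator.** Section 14.3.1 calls the plan feasible if 60% or more of those initially enrolled start vaccination. Patients who progress or have complications after the operation and are judged unfit for vaccine "will not initiate vaccination and will be included in the feasibility analysis". Withdrawals unrelated to surgical morbidity or progression are left out. Section 14 sets the rule at nine of fifteen patients receiving six vaccinations, with a 45% null, one-sided level 0.18 and 75% power.

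**The concern.** The two sets of sections cannot both be followed. Someone screened before surgery cannot yet have recovered from it, so a registrar who applies 4.2 to the whole of Section 3 must wait until after the operation. Some patients whom 14.3.1 intends to count would by then have failed 3.1.5, 3.2.7 or 3.2.8. They would not be registered, their places among the fifteen would go to others, and the feasibility rate would be too high. The plan does not define enrolment relative to either registration or resection, so nothing in the text settles the matter.

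Feasibility is a primary endpoint in 14.1 and the only one with a null, a significance level and power. With fifteen patients, one or two uncounted failures matter.

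**Working it through.** **1. Side by side.**

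- Before surgery: 1.1 (resection still to come), 3.1 (criteria met before the planned resection), 14.3.1 (failures after surgery are counted, so those patients must already be enrolled).
- After surgery: 4.2 combined with 3.1.5 (recovered from resection). 3.2.10 counts time since resection and makes sense only if screening can follow it.
- Open: 4.1 (before therapy only). 3.2.7 and the residual-disease part of 3.2.8 can be judged only at or after surgery.

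**2. The plan's own figures.** Inputs from Section 14: n = 15, pass if X ≥ 9, null 0.45. The 65% rate there is taken as the alternative, although it is not labelled so. With

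P(X ≥ 9) = Σ (k = 9 to 15) C(15,k) p^k (1−p)^(15−k),

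p = 0.45 gives 0.1818 and p = 0.65 gives 0.7548. The stated 0.18 and 75% are reproduced.

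**3. Effect of unregistered losses.** Let f be the share of planned-resection patients who fail early and are never registered. All of them are failures, so the success rate among the registered is p/(1−f). The documents give no value for f; 5% to 15% is an assumption. Take p = 0.45 from planned resection:

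| f | Rate among registered | P(at least 9 of 15) | Planned resections needed for 15 registered |
|---|---|---|---|
| 0 | 0.450 | 0.18 | 15 |
| 5% | 0.45/0.95 = 0.474 | 0.24 | 15/0.95 = 15.8 |
| 10% | 0.45/0.90 = 0.500 | 0.30 | 15/0.90 = 16.7 |
| 15% | 0.45/0.85 = 0.529 | 0.39 | 15/0.85 = 17.6 |

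These losses amount to about one to three uncounted patients (15.8 − 15 = 0.8 up to 17.6 − 15 = 2.6).

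**4. Effect on an observed result.** Nine successes in fifteen is 60%, exactly the threshold in 14.3.1. Counting one, two or three unregistered failures gives 9/16 = 56%, 9/17 = 53% or 9/18 = 50%. One patient is enough to cross the line.

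**5. Which failures could be lost.** Too few cells is not an eligibility criterion, so it is never filtered out. 3.1.4 and 3.1.6 are worded as conditions for receiving vaccine. If 3.2.10 applies at registration, registration falls within about one month of surgery. Section 5.1.2 allows vaccination to start up to six months after surgery, so later failures would occur in registered patients and be counted. Only losses at surgery or in roughly the first month are exposed.

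**The case against.** The best reply is that the trial-specific text already places enrolment before surgery and that 4.1 and 4.2 are general registration wording. Besides 1.1, 3.1 and 14.3.1, the study calendar times staging scans and infectious-disease tests relative to tumor harvest and liver resection, and 4.1 foresees registered patients who never receive therapy. Section 4.2 refers to the criteria on a checklist that is not in the documents and may already separate the pre-vaccine items. The exclusions apply to conditions present at screening, so someone not yet operated on does not clearly fail 3.2.7 or 3.2.8. Section 14 also speaks of making vaccine from resected metastases, so leaving out patients who prove unresectable could be a deliberate choice.

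Much of this stands. It shows that loss from the denominator is a risk created by conflicting text, not the plan's stated rule. It does not remove the conflict: 3.1.5 still cannot be met when 3.1 says it must be. Nor does it settle what happens to a patient excluded under 3.2.7 during the operation, because 14.3.1 speaks only of failures between surgery and vaccination. If leaving such patients out is intended, the plan should say so.

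A reader might infer that the fifteen would all be patients who recovered and stayed free of disease. The documents do not support that, because low cell yield and failures after about a month remain counted. A reader might also assume losses of 20% or 30%, which would put the chance of passing at 0.49 or 0.74. Nothing in the documents supports losses of that size from the early period alone.

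**Conclusion.** The concern holds as an unresolved conflict over when patients are registered, with a possible upward bias in the feasibility rate. The bias is confined to patients who fail at surgery or soon after it, and it is zero if all patients are registered before resection and their later failures are counted.

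The figures of 0.24 to 0.39 against a nominal 0.18 rest on three assumptions: that 5% to 15% of planned-resection patients are lost unregistered, that the 45% null refers to success from planned resection (Section 14 does not say so), and that outcomes are independent. They use Section 14's six-vaccination rule. Section 14.3.1 counts a first vaccination instead. That difference in the numerator is a separate matter, but the denominator question affects both rules. The point should be settled because the endpoint is primary and its 60% threshold can turn on one uncounted patient.

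**What to change.** - In 4.1 and 14.3.1, state that registration takes place before the hepatic resection and that enrolled means registered.
- Split Section 3 and the checklist into criteria for registration and criteria checked at surgery or before the first vaccine (3.1.4 to 3.1.6, 3.2.7, 3.2.8), without changing any threshold.
- Define the feasibility denominator as all patients registered before resection. Count those who later fail the second list as not vaccinated. Keep 14.3.1's existing exclusion of unrelated withdrawals.
- Do not move 3.2.10 to the second list. Next to the four-week minimum after the operation (3.1.6; 5.1.2.4 says more than 28 days), a one-month limit would leave about 31 − 28 = 3 days for the first vaccine. It would also clash with the six-month start window in 5.1.2. These sections must be reconciled by the sponsor and the investigator.

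The cost is wording in Sections 3, 4 and 14.3.1 and a revised checklist. The reported feasibility rate may be lower, and some of the fifteen places will go to patients who are never vaccinated.
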